#### 6.15.5 Serological Testing

Blood samples will be collected at Screening and LFU, and sent frozen to the central laboratory for serologic tests for *M. pneumoniae*, *C. pneumoniae*, and *L. pneumophila*.

#### 6.15.6 Urine Antigen Test

A urine sample will be taken at Screening and tested at the clinical site for *L. pneumophila* and *S. pneumoniae* antigen. Results will be recorded in the eCRF. Clinical sites that are unable to perform urinary antigen testing will send urine to the central laboratory for testing. Subjects who have urinary antigen test positive for *L. pneumophila* at Screening, or sites that are sending urine to the central laboratory for urinary antigen testing, will have a portion of the sputum sample collected at Screening sent to the central laboratory for *L. pneumophila* testing as described above (Section 6.15.1).

## 6.15.7 Oropharyngeal Specimen

An oropharyngeal specimen (2 swabs) will be obtained at Screening and sent to the central laboratory/specialty laboratory for *M. pneumoniae* culture, susceptibility testing, as well as identification by PCR. Oropharyngeal specimens must be frozen until shipment to the central laboratory.

## 6.15.8 Nasopharyngeal Specimen

A nasopharyngeal specimen (1 swab) will be obtained at Screening and sent to the central laboratory/specialty laboratory for *S. pneumoniae* culture, susceptibility testing, as well as identification by PCR. Culture, susceptibility testing, as well as identification by PCR may also be performed for *H. influenzae*. Nasopharyngeal specimens must be frozen until shipment to the central laboratory.

## 6.16 Health Utilization and Patient Reported Outcome

Exploratory evaluation of a variety of health utilization variables (e.g., length of hospital stay, duration of antibiotic therapy, discharge status, discharge destination) as well as a PRO instrument (SF-12) will be administered. Details for this exploratory analysis will be presented in a separate SAP and results will be presented in a stand-alone clinical study report.

## 6.17 Food and Beverage Restrictions

Subjects should refrain from drinking alcohol throughout study drug administration period.

In addition, as discussed in Section 5.4, study drug should be administered at least 1 hour before a meal or 2 hours after a meal. However, in the event that a subject has taken any of the following – antacids containing aluminum, products containing iron, or multivitamins containing zinc – study drug should be administered 2 hours before or 4 hours after consuming any of these medications.

# 6.18 Discontinuation from Treatment or Study

Subjects are free to withdraw from the study at any time for any reason. Subjects may be withdrawn from study at the discretion of the Principal Investigator or Sub-Investigator at any time. Once a subject has been withdrawn from the study they may not be re-entered. Subjects who withdraw or who are withdrawn from the study will not be replaced. If a subject is discontinued from treatment or from the study, the reason for discontinuation will be collected in the eCRF.

#### 6.18.1 Discontinuation from Treatment

A subject may be discontinued prematurely from study drug treatment for the following reasons:

- Lack of efficacy (i.e., requirement for additional non-study antibacterial therapy to treat the current episode of CABP)
- Adverse event
- Withdrawal by subject [specify reason in the eCRF]
- Lost to follow-up

- Physician decision (i.e., Investigator decision based on protocol violation, assessment that it is not in the subject's best interest to continue, or other reason) [specify reason in the eCRF]
- Sponsor decision [specify reason in the eCRF]

If a subject is prematurely withdrawn from study drug treatment, the Investigator should make every effort to retain the subject in the study and perform all procedures scheduled for the EOT, TOC, and LFU visits. Any subject withdrawn from treatment due to an AE, SAE, or clinically significant abnormal laboratory test value will be evaluated by the Investigator, or a monitoring physician, and will be treated and/or followed up until the symptoms or values have either resolved or are assessed as stable by the Investigator.

#### 6.18.2 Discontinuation from Study

A subject may be discontinued prematurely from the study for the following reasons:

- Withdrawal by subject [specify reason in the eCRF]
- Lost to follow-up
- Death
- Physician decision (i.e., assessment that it is not in the subject's best interest to continue, or other reason) [specify reason in the eCRF]
- Sponsor decision [specify reason in the eCRF]

Every attempt will be made to contact subjects who withdraw from the study in order to determine their vital status (alive or dead) at Day 28.

## 6.18.3 Individual Stopping Criteria

Subjects will be withdrawn from the study drug treatment for any of the following reasons:

- The subject demonstrates an average QTcF value > 500 ms (mean of 3 ECG's at any time point) as assessed locally by the Investigator. Such subjects should be observed until the ECG normalizes with repeat ECG's taken at the discretion of the investigator.
- The subject demonstrates an average QTcF value > 480 ms with a concurrent increase in average QTcF value of > 60 ms (mean of 3 post-dose ECGs compared to mean pre-dose ECGs taken on that day) as assessed locally by the Investigator.
- The subject has confirmed *S. aureus* bacteremia.

If a subject is prematurely withdrawn from study treatment, the Investigator should make every effort to retain the subject in the study and to perform all procedures scheduled for the EOT, TOC, and LFU visits. Any subject withdrawn from treatment due to an AE, SAE, or clinically significant abnormal laboratory test value will be evaluated by the Investigator, or a

monitoring physician, and will be treated and/or followed up until the symptoms or values have either resolved or are assessed as stable by the Investigator.

#### 6.18.4 Lost to Follow-up

Every reasonable attempt should be made to retain subjects in the study. If a subject does not report to the study site for a scheduled visit, study personnel will make 4 contact attempts: 3 telephone contact attempts and, if these are unsuccessful, a certified letter will be sent to the subject. The subject will be considered lost to follow-up if (1) upon receipt of delivery confirmation of the certified letter the subject does not contact the site or (2) the certified letter is returned as undeliverable. Every attempt will be made to contact subjects who withdraw from the study in order to determine their status (alive or dead) at Day 28.

## 7 ADVERSE EVENTS

An adverse event (AE) is any untoward medical occurrence in a subject or clinical investigation subject administered a pharmaceutical product that does not necessarily have a causal relationship with this treatment. An AE can therefore be any unfavorable and unintended sign (including an abnormal laboratory finding), symptom, or disease temporally associated with the use of an investigational product, whether or not related to the investigational medicinal product.

Any pre-existing conditions or signs and/or symptoms present in a subject prior to the start of the study (i.e., before informed consent) should be recorded as medical/surgical history. Any medical occurrences which are new or worsened from the time of informed consent and up to and including the final visit must be reported as AEs or SAEs. All AEs and SAEs must be recorded irrespective of whether they are considered drug related. NOTE: lack of efficacy/clinical failure does not have to be recorded as an AE unless it is an SAE.

Subjects will be monitored throughout the study for adverse reactions to the study medications and/or procedures at each study visit. Questions will be posed in a non-leading manner so as not to bias the response. In addition to questioning at specific time points, subjects will be encouraged to spontaneously report any AEs. Any subject with an AE, SAE or clinically significant abnormal laboratory test value will be evaluated by the Investigator, or a monitoring physician, and will be treated and/or followed up until the symptoms or values have resolved or are assessed as stable by the by the Investigator. A physician, either at the Investigative site or at a nearby hospital emergency room, will administer treatment of any SAEs. Where appropriate, medical tests and examinations may be performed to ensure that an AE has fully resolved.

Adverse events will be monitored throughout the study from the time a subject is consented through the TOC visit; SAEs are to be collected from the time of consent through the LFU visit. Study personnel will monitor AEs for subjects who are Outpatients in conjunction with daily telephone contacts for CABP signs/symptoms as well as at all site visits (see Table 1). Study personnel will follow unresolved AEs and SAEs present at LFU until resolution or stabilization.

Whenever possible, a specific disease or syndrome rather than individual associated signs and symptoms should be identified by the Investigator and recorded on the subject's eCRF. However, if an observed or reported sign or symptom is not considered a component of a specific disease or syndrome by the Investigator, it should be recorded as a separate AE on the subject's eCRF.

Each AE or SAE reported will be assessed for intensity and the date and time of onset (if available), time relationship to dosing, duration, and outcome of each event will be noted.

Laboratory abnormalities are not considered AEs unless they are associated with clinical signs and symptoms or require medical intervention. Clinically significant abnormal clinical laboratory findings or other abnormal assessments that are associated with the disease being studied, unless judged by the Investigator as more severe than expected for the subject's condition, or that are present or detected at the start of the study and do not worsen, will not be reported as AEs or SAEs.

The Investigator will exercise medical and scientific judgment in deciding whether an abnormal clinical laboratory finding or other abnormal assessment is clinically significant.

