#### 7.3 Serious Adverse Events

An SAE is any untoward medical occurrence that:

- Results in death.
- Is life-threatening. NOTE: The term 'life threatening' in the definition of "serious" refers to an event in which the subject was at risk of death at the time of the event; it does not refer to an event which hypothetically might have caused death if it was more severe.
- Results in persistent or significant disability/incapacity.
- Requires in subject hospitalization or prolongation of existing hospitalization. NOTE: Hospitalizations, which are the result of elective or previously scheduled surgery for pre-existing conditions, which have not worsened after entry into the study, should not be classified as SAEs. For example, admission for a previously scheduled ventral hernia repair would not be classified as an SAE; however, complication(s) resulting from a hospitalization for an elective or previously scheduled surgery that meet(s) serious criteria must be reported as SAE(s).
- Is a congenital anomaly/birth defect.
- Is an important medical event.

NOTE: Medical or scientific judgment should be exercised in deciding whether reporting is appropriate in other situations, such as important medical events that may not be immediately life threatening or result in death or hospitalization but may jeopardize the subject or may require medical or surgical intervention to prevent one of the other outcomes listed in the above definition. These should also be considered serious. Examples of such events are invasive or malignant cancers, intensive treatment in an emergency room or at home for allergic bronchospasm, blood dyscrasias, or convulsions that do not result in hospitalization, or development of drug dependency or drug abuse.

All SAEs will be collected from the time of informed consent until 30 days after the last study treatment regardless of study drug relationship, and must be reported to Nabriva Therapeutics AG or their representative (Covance Pharmacovigilance & Drug Safety Services [PV & DSS]) within 24 hours of knowledge of the event (this refers to any AE that meets one or more of the aforementioned serious criteria).

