#### 7.4 Symptoms of the Disease Under Study

In this study, clinical signs and symptoms of pneumonia which are assessed daily per protocol (i.e., dyspnea, cough, sputum production, and chest pain) will not be reported as adverse events unless they meet the definition of a serious adverse event.

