## 6.6 Safety Outcomes

Safety will be assessed by analysis of AEs and changes in laboratory parameters (chemistry and hematology), electrocardiogram (ECG) parameters, and vital signs. Laboratory abnormalities are not considered AEs unless they are associated with clinical signs and symptoms or require medical intervention. Clinically significant abnormal clinical laboratory findings or other abnormal assessments that are associated with the disease being studied, unless judged by the Investigator as more severe than expected for the subject's condition, or that are present or detected at the start of the study and do not worsen, will not be reported as AEs or SAEs.

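### Protocol Section 7 and SAP 6.6 keep disease-associated abnormal findings of expected severity out of SAE reporting with no override for seriousness, which conflicts with Sections 7.3 and 7.4 and with Section 7's own note on clinical failure

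*Protocol*

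**What the plan says.** The exempting sentence closes the paragraph on laboratory abnormalities in Protocol Section 7. Its subject is "Clinically significant abnormal clinical laboratory findings or other abnormal assessments that are associated with the disease being studied". These are exempt "unless judged by the Investigator as more severe than expected for the subject's condition". A second limb covers findings "present or detected at the start of the study and do not worsen, will not be reported as AEs or SAEs". The final words apply to both limbs. SAP 6.6 carries the same sentence, ending "will not be reported as AEs or SAEs".

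Three neighbouring rules treat seriousness differently:

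- Section 7, on treatment failure: "lack of efficacy/clinical failure does not have to be recorded as an AE unless it is an SAE".
- Section 7.4, on dyspnea, cough, sputum production and chest pain: these "will not be reported as adverse events unless they meet the definition of a serious adverse event".
- Section 7.3: "All SAEs will be collected from the time of informed consent until 30 days after the last study treatment regardless of study drug relationship". It makes no exception for findings related to the disease.

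Section 7 also requires occurrences that are new or worsened after consent to be reported. Where possible, it says, "a specific disease or syndrome rather than individual associated signs and symptoms should be identified by the Investigator".

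**The concern.** Severity and seriousness are separate concepts in this protocol. Section 7.1 grades intensity, while Section 7.3 defines seriousness by outcome, such as death, threat to life, or hospitalization or its prolongation. In moderately severe pneumonia an abnormal finding can be no worse than expected and still lead to admission. The exempting sentence asks only the first question and then removes the finding from SAE reporting by name.

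A site with such a finding has one specific sentence telling it not to report and a general rule telling it to report. What is at stake is the 24-hour report to the sponsor under Section 7.3 and the serious TEAE table in SAP 8.7.1, which counts only what sites report. Two sites could handle the same finding differently and each could point to the protocol.

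**Working it through.** No arithmetic applies. The check sets the rules side by side and then follows one case through them.

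| Place | What is exempt | Condition that restores reporting |
|---|---|---|
| Protocol 7, note on clinical failure | Lack of efficacy or clinical failure | It is an SAE |
| Protocol 7.4 | Four daily-assessed pneumonia symptoms | It meets the SAE definition |
| Protocol 7, exempting sentence, first limb | Disease-associated abnormal laboratory findings and other abnormal assessments | Investigator judges it more severe than expected |
| SAP 6.6 | Same as the row above | Same as the row above |
| Protocol 7.3 | Nothing disease-related | Not applicable: all SAEs are collected |

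Two of the three disease-related exemptions use seriousness as the override. The third uses expected severity alone.

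Is there a case that only the third rule governs? Take an outpatient whose oxygen saturation falls, who is admitted without a change of antibacterial, and whose Investigator regards the fall as within what this pneumonia would produce.

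1. *Can it be an AE?* Yes. Section 7 defines an AE to include an unfavorable sign, and oxygen saturation is a scheduled assessment in Table 1.
2. *Is it serious?* Yes. Hospitalization is a Section 7.3 criterion, so Section 7.3 says collect it.
3. *Does Section 7.4 restore it?* Not by itself. Saturation, temperature, blood pressure and white cell count are not among the four symptoms listed. If the subject also becomes breathless at rest or needs oxygen, Table 4 grades that as severe dyspnea, and Section 7.4 then applies.
4. *Does the clinical-failure note restore it?* Not if failure is read as in Section 6.12.1. Apart from death, every criterion there involves starting non-study antibacterial therapy.
5. *Does the exempting sentence apply?* On its wording, yes: the finding is an abnormal assessment, associated with the disease, and no more severe than expected. It says do not report as an SAE.

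Steps 2 and 5 give opposite instructions. Hypotension of expected severity that prolongs a hospital stay takes the same path.

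Would other outputs recover an unreported finding? Partly. SAP 8.7.2 analyses laboratory values whether or not they are AEs, through potentially clinically significant values, shift tables and Hy's Law listings. SAP 8.7.4 covers temperature, respiratory rate, heart rate and blood pressure, but its summaries do not include oxygen saturation. None of these outputs classifies an event as serious.

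**The case against.** The strongest answer is that the sentence concerns findings, not events. A patient admitted with worsening pneumonia has had a medical occurrence, which Section 7 requires to be reported as new or worsened. If it is a clinical failure and serious, the note in Section 7 covers it; if it shows as one of the four symptoms, Section 7.4 does. The preference for recording the disease over its component signs then suggests a coherent reading: report the event and do not list each abnormal value as its own AE or SAE. The severity exception also narrows the exemption. Inclusion criterion 7 admits only suitable candidates for oral therapy, so a finding that leads to admission may well be judged worse than expected.

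Much of this stands. It is why most serious deteriorations stay reportable and why the gap is small.

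It does not close the gap. The reconciling reading is sensible, but the protocol does not state it. The preference for naming a disease governs how an event is recorded, not whether it must be reported when serious. Whether an admission implies worse-than-expected severity is left to individual judgement, and PORT Risk Class IV subjects and inpatients are eligible. Section 7.3 does invite medical judgement about important medical events, but the question there is whether an event is serious, not whether its severity was expected.

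**Conclusion.** The conflict is real and narrow. It concerns disease-associated abnormal laboratory findings or assessments that are judged no more severe than expected, meet a Section 7.3 criterion, and are captured neither as clinical failure nor as one of the four symptoms in Section 7.4. For these, Section 7 and SAP 6.6 say not to report and Section 7.3 says to collect.

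Four stronger readings are tempting, and the documents do not support them.

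- *That serious deteriorations of pneumonia in general can go unreported.* The general rule in Section 7, its clinical-failure note, and Sections 7.3 and 7.4 keep most of them in.
- *That the limb on findings present at the start exempts a deterioration.* That limb is confined to findings that do not worsen. The conflict lies in the disease-associated limb.
- *That the number of lost SAEs can be derived from the planned 80% IACR success rate in mITT.* The remaining 20% mixes indeterminate outcomes with failures that are already reportable when serious, and the documents give no rate for the findings in question. The effect on the serious TEAE table cannot be quantified.
- *That the DMC would see incomplete data.* What it receives is set by a Charter that is not among the documents.

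The conclusion rests on a literal reading of the sentence and on the undefined term for other assessments including scheduled measurements such as oxygen saturation and blood pressure.

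**What to change.** Keep the sentence in Protocol Section 7 and SAP 6.6, and add to the limb on disease-associated findings: *unless the finding meets a seriousness criterion in Section 7.3, in which case it is reported as an SAE*. This follows the model the protocol already uses for clinical failure and for pneumonia symptoms, and brings the sentence into line with Section 7.3. The limb on unchanged baseline findings can stay as it is, since Section 7 already treats conditions present before consent as medical history.

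The cost is one clause in each document, a notice to sites, and a few more SAE reports. Endpoints, sample size and the efficacy analyses are unaffected.

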# 7.1 Assessment of Severity (Intensity)

The following definitions for rating severity (intensity) will be used:

Mild: A type of AE that is usually transient and may require only minimal

treatment or therapeutic intervention. The event does not generally interfere

with usual activities of daily living

**Moderate**: A type of AE that is usually alleviated with specific therapeutic intervention.

The event interferes with usual activities of daily living, causing discomfort

but the subject is still able to function

**Severe**: The type of AE that interrupts usual activities of daily living, or significantly

affects clinical status, or may require intensive therapeutic intervention.

# 7.2 Assessment of Relationship to Study Drug

The Investigator will use his/her clinical judgment to explain each adverse event and determine its relationship, if any, to study drug treatment. Alternative causes, such as natural history of the underlying diseases, concomitant therapy, other risk factors, and the temporal relationship of the event to the study drug will be considered and investigated. The Investigator will also consult the Investigator's Brochure in the determination of his/her assessment. Causality should be assessed using the following categories:

**Not related** The event could readily be explained by factors not involving the study

drug and a temporal relationship with the study drug did not exist.

**Possibly Related** There was some temporal relationship between the event and the

administration of the study drug and the event was unlikely to be explained by the subject's medical condition or other therapies.

**Probably Related** The temporal relationship between the event and the administration of

the study drug was suggestive, and the event was less likely to be

explained by the subject's medical condition or other therapies.

**Definitely Related** The event followed a reasonable temporal sequence from administration of the study drug, followed a known or suspected

response pattern to the study drug, was confirmed by improvement upon stopping the study drug (dechallenge) and reappeared upon repeated exposure (rechallenge). (NOTE: this was not to be construed as requiring re-exposure of the subject, however, a category of

definitely related could only be used when recurrence was observed.).

